3.0 Introduction

This statistical analysis plan (SAP) describes the statistical analysis to be completed by the AbbVie Global Statistics Department for study Protocol M14-033 Amendment 3 dated 16 June 2016. It provides details to further elaborate statistical methods as outlined in the protocol and describes analysis conventions to guide the statistical programming work.

This is the first version of SAP for the 44-Week Double-Blind Maintenance Japan Sub-Study of Protocol M14-033.

Study M14-033 consists of a Main Study and a Japan Sub-Study. This SAP version is developed solely for the Maintenance Japan Sub-Study, which is conducted in approximately 21 Japanese sites following the Protocol Amendment 3. All data from subjects enrolled under the Main Study will be excluded from the analyses described in this SAP. A separate SAP will be developed for the Main Study.

This analysis plan describes the primary and secondary efficacy analyses as well as the safety analysis for the Maintenance Study under the Protocol Amendment 3. A separate SAP was developed for the Induction Japan Sub-Study.

Unless noted otherwise, all analyses will be performed using SAS version 9.4 or later (SAS Institute Inc., Cary, NC 27513) under the UNIX operating system.

4.0 Study Objectives, Design and Procedures

4.1 Objectives

The Japan Sub-Study objective is to evaluate the safety and efficacy of higher induction and maintenance dosing regimens in subjects with moderately to severely active ulcerative colitis and to show the consistency of efficacy between Japanese population and integrated population of Japanese and Western subjects from the Main Study.

4.2 Design Diagram

This is a Phase 3, double-blind, randomized, multicenter study of higher versus standard adalimumab dosing regimens for induction and maintenance therapy in subjects with moderately to severely active UC (Mayo Score of 6 to 12 points with an endoscopy subscore of 2 or 3, confirmed by a central reader). For all Mayo Score evaluations throughout the study, the stool frequency and the rectal bleeding subscores will be calculated based on entries recorded in daily electronic patient diaries.

The Japan Sub-Study was designed to enroll 100 Japanese subjects (60 subjects in the higher induction dose regimen and 40 subjects in the standard induction dose regimen) at approximately 21 sites in Japan to meet scientific and regulatory objectives without enrolling an undue number of subjects in alignment with ethical considerations. There are also 840 subjects in a Main Study to be enrolled at 125 sites worldwide outside Japan.

[figure not shown]
This study will include:

- An up to 21 days Screening Period
- An 8-Week Double-Blind Induction Study
- A 44-Week Double-Blind Maintenance Study
- A 70-Day Follow-Up Period

During both the Induction Study and the Maintenance Study, visit week designations will represent weeks since first adalimumab dose in the Induction Study. Week 0 (Baseline) will reflect the date of first adalimumab dosing in the Induction Study. Week 8 will represent the final assessment in the Induction Study and the beginning of the Maintenance Study. Week 52 will represent the final assessment in the Maintenance Study (representing 44 weeks of maintenance treatment in the Maintenance Study). A subject's participation in the study is anticipated to be up to 65 weeks. There is a \pm 3 day window for all study visits. An effort will be made to bring subjects back to their original scheduled visit (calculated from Baseline) if they are out of the visit window.

A schematic of the study design is presented in [Figure 1](#).

Figure 1. Study Schematic (Japan Sub-Study)

8-Week Double-Blind Induction Study

[figure not shown]
Subjects who met all of the inclusion criteria and none of the exclusion criteria were to be enrolled into the 8-Week Induction Study. The Main Study and the Japan Sub-Study would each allow enrollment of up to 25% of subjects with previous infliximab exposure.

Subjects were to be randomized via interactive response system (IRT) at Baseline (Week 0) to one of 2 double-blinded adalimumab induction regimens (higher dose or standard dose) in a 3:2 ratio. Use of the 3:2 randomization scheme allows for collection of additional safety data with the higher induction dose regimen. The randomization was to be stratified by:

- Previous infliximab use, and
- Baseline corticosteroid use.

The higher induction dose regimen of 160 mg at Weeks 0, 1, 2, and 3, followed by 40 mg at Weeks 4 and 6 leads to a total adalimumab dose over 8 weeks that is approximately twice that of the standard induction regimen (720 mg versus 320 mg) as shown in Figure 2 below.

Figure 2. 8-Week Double-Blind Induction Study

Subjects would return to the study site at scheduled visits and complete study procedures for each visit.

At Week 4, all subjects who were on oral corticosteroids at Baseline would have their corticosteroid dose tapered according to the proposed tapering schedule outlined in the protocol. If the Investigator felt that the steroid taper was not advisable for a particular subject at Week 4, the SDP should have been consulted for evaluation and approval.

44-Week Double-Blind Maintenance Study

The TDM regimen in the maintenance period will not be applied to the Japan Sub-Study because of logistical challenges in obtaining adalimumab serum concentration results

within the time period specified in the Main Study. At the conclusion of the 8-Week Double-Blind Induction Japan Sub-Study, subjects will return to the study site and will be re-randomized via IRT into the 44-Week Double-Blind Maintenance Japan Sub-Study to one of two treatment groups in a 1:1 ratio:

- Adalimumab 40 mg eow.
- Adalimumab 40 mg every week (ew).

Subjects in the adalimumab 40 mg eow treatment group will continue to receive 40 mg eow until the end of the study. Subjects in the adalimumab 40 mg ew treatment group will start 40 mg ew at Week 8 until the end of the study.

70-Day Follow-Up/Premature Discontinuation

Subjects may discontinue adalimumab treatment at any time during study participation. Subjects who end study participation early will have a premature discontinuation (PD) Visit. Subjects will have a follow-up phone call approximately 70 days after the last administration of study drug to obtain information on any new or ongoing AEs. The 70 day follow-up phone call will not be required for any subject who initiates commercial adalimumab.

4.3 Sample Size

One hundred Japanese subjects have been determined as the proper sample size for the Japan Sub-Study based on the following rationale. Using the same assumptions as the Main Study with the following:

- Remission rate for induction treatment at 8 weeks: 35% in the high dose group and 20% in the standard dose group
- Remission rate for maintenance treatment at 52 weeks among Week 8 responders: 48% in the high dose group and 30% in the standard dose group
- Overall response rate for induction treatment at Week 8: 50%
- $\alpha = 5\%$, power = 95% for induction study
- $\alpha = 5\%$, power = 90% for maintenance study

The precisions of point estimations of remission rates in Japanese population are included within the 95% CI of remission rates in integrated population will be within 20% with 100 subjects. With this sample size, the probability to show consistency between Japanese population and integrated population will be greater than 80% using the method 2 shown in the "Basic principles on global clinical trials."

4.4 Final Analysis of Maintenance Study

The final analysis of the primary endpoint, ranked secondary efficacy variables and additional efficacy variables as well as safety data will be performed after the last subject in the I-ITT (Section 5.1 for definition) population completes the 44-week double-blind Maintenance Study. A database lock will be performed and any discrepant data will be clarified before the lock. The statistical methods for the analysis of the primary endpoint are outlined in Section 10.2. The statistical methods for the analyses of the ranked secondary efficacy endpoints are outlined in Section 10.3.

4.5 Derived, Defined and Transformed Variables

The following defined variables will be used:

- **Full Mayo Score**

- Full Mayo Score is defined as the composite score of UC disease activity based on the subscores of stool frequency (0 – 3), rectal bleeding (0 – 3), physician's global assessment (0 – 3) and endoscopy (0 – 3). This score ranges from 0 – 12 points with higher scores representing more severe disease (also see Section 6.0 for the rules for calculation of rectal bleeding and stool frequency subscores).
- Clinical Response is defined as a decrease in Full Mayo Score of ≥ 3 points and $\geq 30\%$ from Baseline, PLUS a decrease in the rectal bleeding subscore [RBS] ≥ 1 or an absolute RBS ≤ 1 .
- Clinical Remission is defined as Full Mayo Score ≤ 2 with no subscore > 1 .

- **Partial Mayo Score**

- Partial Mayo Score is defined as the composite score of UC disease activity based on the subscores of stool frequency, rectal bleeding, and physician's global assessment and DOES NOT include the endoscopy subscore. This score ranges from 0 – 9 points also see Section 6.0 for the rules for calculation of rectal bleeding and stool frequency subscores.
- Clinical Response per Partial Mayo Score is defined as a decrease in Partial Mayo Score ≥ 2 points and $\geq 30\%$ from Baseline, PLUS a decrease in RBS ≥ 1 or an absolute RBS ≤ 1 .
- Clinical Remission per Partial Mayo Score is defined as Partial Mayo Score ≤ 2 , with no subscore > 1 .

- **Adapted Mayo Score**

- Adapted Mayo Score is defined as Full Mayo Score minus the Physician's Global Assessment (PGA) subscore.
- Clinical Remission per Adapted Mayo Score is defined as an Adapted Mayo Score ≤ 2 , with stool frequency subscore ≤ 1 , RBS of 0, and endoscopic subscore ≤ 1 .
- Clinical Response per Adapted Mayo Score is defined as a decrease in the Adapted Mayo Score ≥ 2 points and $\geq 30\%$ from baseline, PLUS a decrease in RBS ≥ 1 or an absolute RBS ≤ 1 .

- **IBDQ Response**

- IBDQ Response is defined as at least a 16-point increase from Baseline in total Inflammatory Bowel Disease Questionnaire (IBDQ) score.

- **Endoscopic Improvement:** endoscopy subscore of 0 or 1.
- **Endoscopic Remission:** endoscopy subscore of 0.
- **Histologic Improvement:** decrease in Geboes score from Baseline
- **Histologic Remission:** Geboes score < 2.0

5.0 Analysis Populations

5.1 Definition for Analysis Populations

The Japanese population is defined as all Japanese subjects who were randomized at sites in Japan. The following populations will be used for analyses in Japan Sub-Study:

Integrated Intent-to-Treat maintenance (I-ITT) population includes all subjects who are re-randomized at both Japanese sites and all other sites in the Main Study at Week 8 into the Maintenance Study. The Japan ITT (J-ITT) dataset includes all Japanese subjects who are re-randomized at Japanese sites at Week 8 into the Maintenance Study. I-ITT and J-ITT subjects will be analyzed as randomized.

Integrated ITT-Responder (I-ITT-RP) population includes all subjects in I-ITT who achieve Week 8 response based on the Full Mayo Score utilizing the endoscopy subscore provided by the central reader. Japan ITT-Responder (J-ITT-RP) population includes all subjects in J-ITT who achieve Week 8 response based on the Full Mayo Score utilizing the endoscopy subscore provided by the central reader. I-ITT-RP and J-ITT-RP are the populations for the efficacy analysis of Week 8 responders during the Maintenance Study.

Integrated ITT-Non-Responder (I-ITT-NRP) population includes all subjects in I-ITT who do not achieve Week 8 response based on the Full Mayo Score utilizing the endoscopy subscore provided by the central reader. Japan ITT-Non-Responder (J-ITT-NRP) population includes all subjects in J-ITT who do not achieve Week 8 response based on the Full Mayo Score utilizing the endoscopy subscore provided by the central reader. ITT-NRP is the population for the efficacy analysis of Week 8 non-responders during the Maintenance Study.

Integrated ITT-Remitter (I-ITT-RM) population includes all subjects in I-ITT who achieve Week 8 remission based on the Full Mayo Score utilizing the endoscopy subscore provided by the central reader. Japan ITT-Remitter (J-ITT-RM) population includes all subjects in J-ITT who achieve Week 8 remission based on the Full Mayo Score utilizing

the endoscopy subscore provided by the central reader. I-ITT-RM and J- ITT-RM is the population for the efficacy analysis of Week 8 remitters during the Maintenance Study.

Integrated ITT-Non-Remitter (I-ITT-NRM) population includes all subjects in I-ITT who do not achieve Week 8 remission based on the Full Mayo Score utilizing the endoscopy subscore provided by the central reader. Japan ITT-Non-Remitter (J-ITT-NRM) population includes all subjects in J-ITT who do not achieve Week 8 remission based on the Full Mayo Score utilizing the endoscopy subscore provided by the central reader. I-ITT-NRM and J- ITT-NRM are the populations for the efficacy analysis of Week 8 non-remitters during the Maintenance Study.

The integrated safety set for Maintenance Study consists of all subjects (from both Japanese sites and sites in the Main Study) who received at least one dose of study drug in the Maintenance Study. The Japan safety set for Maintenance Study consists of all Japanese subjects from Japanese sites who received at least one dose of study drug in the Maintenance Study. The integrated safety set and Japan safety set for Maintenance Study will be analyzed as treated, according to treatment the subject actually received.

6.0 Analysis Conventions

Definition of Induction Baseline

The induction baseline (hereafter referred to as Baseline) visit date is the date when the first dose of study drug is received during Induction Study and referred to as Day 1 or Week 0. The baseline value for a variable is defined as the last non-missing value on or before the date of the first dose of study drug during Induction Study.

Definition of Maintenance Baseline

The maintenance baseline visit date is the date when the first dose of study drug is received during Maintenance Study. The maintenance baseline value for a variable is defined as the last non-missing value on or before the date of the first dose of study drug during Maintenance Study.

Definition of Final Observation

Final Observation in Maintenance Study is defined as the last non-missing observation collected within 70 days following the last dose of study drug for subjects who are re-randomized. The 70-day follow-up phone call will not be required for any subject who initiates commercial adalimumab.

Definition of Rx Days (Days Relative to the First Dose of Maintenance Study Drug)

Rx Day during the Maintenance Study is calculated as the event date minus the date of first dose of the Maintenance Study drug plus 1. The Rx Day will be a negative value

when the time point of interest is prior to the date of first dose of study drug, and the Rx Day will be a positive value when the time point of interest is after the first dose date. Rx days are used to map actual study visits to the protocol specified study visits during Maintenance Study, as defined below. If a subject has not taken any study drug during Maintenance Study, Rx Day during the Maintenance Study will be calculated as the event date minus the date of re-randomization date plus 1.

Definition of Analysis Windows

Since subjects do not always adhere to the study visit schedule, the following rules will be applied to assign actual visits to protocol-specified visits including early termination visits. For each study visit mentioned in the protocol, a nominal or target day along with a window around the target day will be selected to represent the corresponding visit. Windows will be selected in a non-overlapping fashion so that a date collected on the CRF does not correspond to multiple visit windows. Moreover, windows will not discard any post-baseline measurement recorded on the CRF. If a subject had two or more actual visits in one visit window, the visit closest to the target will be used as the study visit for that window. If two visits are equidistant from the target, then the later visit will be used for reporting. If more than one assessment is collected on the same day, then the average of those assessments will be used in analyses.

Table 1. Visit Windows for Analysis of Efficacy Variables, Laboratory Parameters and Vital Signs (Maintenance Study)

Scheduled Week	Nominal Day	Time Window (Rx Day Range)
Entry of the Maintenance Study (Maintenance Baseline)	1	≤ 1
Week 10 (Week 2 of Maintenance Study)	15	2 – 22
Week 12 (Week 4 of Maintenance Study)	29	23 – 43
Week 16 (Week 8 of Maintenance Study)	57	44 – 78
Week 22 (Week 14 of Maintenance Study)	99	79 – 106
Week 24 (Week 16 of Maintenance Study)	113	107 – 130
Week 29 (Week 21 of Maintenance Study)	148	131 – 169
Week 35 (Week 27 of Maintenance Study)	190	170 – 197
Week 37 (Week 29 of Maintenance Study)	204	198 – 221
Week 42 (Week 34 of Maintenance Study)	239	222 – 260
Week 48 (Week 40 of Maintenance Study)	281	261 – 295
Week 52 (Week 44 of Maintenance Study)	309	296 – 379

Rx Day = date of visit – date of first study drug injection in the Maintenance Study + 1.

Table 2. Visit Windows for Analysis of hs-CRP (Maintenance Study)

Scheduled Week	Nominal Day	Time Window (Rx Day Range)
Entry of the Maintenance Study (Maintenance Baseline)	1	≤ 1
Week 12 (Week 4 of Maintenance Study)	29	2 – 43
Week 16 (Week 8 of Maintenance Study)	57	44 – 85
Week 24 (Week 16 of Maintenance Study)	113	86 – 130
Week 29 (Week 21 of Maintenance Study)	148	131 – 176
Week 37 (Week 29 of Maintenance Study)	204	177 – 221
Week 42 (Week 34 of Maintenance Study)	239	222 – 274
Week 52 (Week 44 of Maintenance Study)	309	275 – 379

Rx Day = date of visit – date of first study drug injection in the Maintenance Study + 1.

Table 3. Visit Windows for Analysis of Fecal Calprotectin (Maintenance Study)

Scheduled Week	Nominal Day	Time Window (Rx Day Range)
Entry of the Maintenance Study (Maintenance Baseline)	1	≤ 1
Week 12 (Week 4 of Maintenance Study)	29	2 – 43
Week 16 (Week 8 of Maintenance Study)	57	44 – 85
Week 24 (Week 16 of Maintenance Study)	113	86 – 159
Week 37 (Week 29 of Maintenance Study)	204	160 – 257
Week 52 (Week 44 of Maintenance Study)	309	258 – 379

Rx Day = date of visit – date of first study drug injection in the Maintenance Study + 1.

Table 4. Visit Windows for Analysis of Endoscopy Variables (Maintenance Study)

Scheduled Week	Nominal Day	Time Window (Rx Day Range)
Entry of maintenance period (Maintenance Baseline)	1	≤ 1
Week 52 (Week 44 of Maintenance Study)	309	113 – 379

Rx Day = date of visit – date of first study drug injection in the Maintenance Study + 1.

Table 5. Visit Windows for Analysis of IBDQ (Maintenance Study)

Scheduled Week	Nominal Day	Time Window (Rx Day Range)
Entry of the Maintenance Study (Maintenance Baseline)	1	≤ 1
Week 12 (Week 4 of Maintenance Study)	29	2 – 71
Week 24 (Week 16 of Maintenance Study)	113	72 – 159
Week 37 (Week 29 of Maintenance Study)	204	160 – 257
Week 52 (Week 44 of Maintenance Study)	309	258 – 379

Rx Day = date of visit – date of first study drug injection in the Maintenance Study + 1.

Table 6. Visit Windows for Analysis of EIM, SF36 and WPAI (Maintenance Study)

Scheduled Week	Nominal Day	Time Window (Rx Day Range)
Entry of maintenance period (Maintenance Baseline)	1	≤ 1
Week 52 (Week 44 of Maintenance Study)	309	113 – 379

Rx Day = date of visit – date of first study drug injection in the Maintenance Study + 1.

Definition of Missing Data Imputation

The following imputation methods will be used to impute missing values in the efficacy analyses. In addition, an observed case analysis will be performed.

Non-Responder Imputation (NRI)

The NRI approach is used for binary efficacy variables. These variables can take values of 'Achieved' or 'Not Achieved,' or may be missing for any reason including discontinuation from study. According to the NRI imputation approach, all missing value will be considered as 'Not Achieved.' In addition, subjects who prematurely discontinue from the study drug will be considered as 'Not Achieved' for all subsequent visits after discontinuation.

Observed Case (OC)

The OC analysis will not impute values for missing evaluations, and thus a subject who does not have an evaluation on a scheduled visit will be excluded from the OC analysis for that visit. In addition, the OC analysis will not use values after premature discontinuation of study drug.

Mixed-Effect Model Repeated Measure (MMRM)

The repeated measure analysis will be conducted using mixed model including observed measurements at all visits. Data collected after premature discontinuation of study drug will be excluded from the analysis. The mixed model includes the categorical fixed

effects of treatment, visit and treatment-by-visit interaction, stratification factors at randomization, and the continuous fixed covariates of baseline measurement. An unstructured variance covariance matrix will be used.

Last Observation Carried Forward (LOCF)

The LOCF rule will be used to impute for missing continuous and categorical efficacy data. Values on or prior Maintenance Baseline will not be used to impute the missing values post Maintenance Baseline. Missing values after Maintenance Baseline will be imputed using the latest non-missing value after Maintenance Baseline and prior to the missing value. If there are no non-missing values after Maintenance Baseline, then the LOCF value will be missing. If a subject has missing values for a specific visit, the data will be imputed using LOCF only for the period which the subject started.

Rules for Calculation of Stool Frequency Subscore and Rectal Bleeding Subscore

The diary entries on the days the subjects take endoscopy preparation medications, the day of endoscopy procedure, and the 2 days after endoscopy procedure will be excluded. For the calculation of the stool frequency subscore and the rectal bleeding subscore at each visit, the most recent 5 available diary days from up to 14 days preceding the visit will be used.

To calculate these subscores when fewer than 5 days of diary data are available in the previous 14 days, the average will be based on the most recent 4 days will be used if only 4 days are available, or the average will be based on the most recent 3 days will be used if only 3 days are available.

If the subject has fewer than 3 days of diary entries, the score for that subject at the visit will be considered missing, and the subject will be categorized as a non-responder (NRI) for any categorical endpoints relating to data for this visit.

Rounding to one decimal place will be applied to the calculation above for the subscores, Partial Mayo Score and Full Mayo Score.

The last day of the 5 days will be used to decide the actual visits that should be assigned to the Mayo Score and Partial Mayo Score data.

Rules for Efficacy Assessment Based on Concomitant Treatment

Subjects in whom the UC-related systemic or rectal corticosteroids that were not being taken at Baseline and are initiated during the study or who have dosages of these medications increased to greater than the dose taken at Baseline will be censored for efficacy assessments (i.e., will be considered non-responders for categorical endpoints and will have last non-missing values carried forward for non-categorical assessments) from that point through the end of the study. These subjects will continue to be evaluated in the integrated safety and Japan safety populations.

The equivalent steroid dose will be determined based on [Table](#) :

Table 7. Equivalent Steroid Dose

Corticosteroid	Equivalent Dose (mg)
Cortisone	25
Hydrocortisone	20
Prednisone	5
Prednisolone	5
Triamcinolone	4.0
Methylprednisolone	4.0
Betamethasone	0.75
Dexamethasone	0.75
Budesonide	1
Beclomethasone	5

Definition of Medication Use at Baseline

Medications are considered to be used at Baseline if the medication start date is on or before the first study drug dose date and the medication end date is on or after the

first dose date. All medications with a start date after the first dose date or an end date before the first dose date are excluded.

Treatment Interruption

If the study drug treatment interruption is longer than 60 days and treatment re-introduction is evaluated as not feasible, the subject will be considered as premature discontinuation from the study in all efficacy assessment after the last dose and all the aforementioned imputation rules apply.

Imputation of Missing Dates

For baseline, efficacy, and safety parameters, if the day and/or month are missing, the following conventions will be used to impute the missing dates:

- 01 for missing start day
- End of month for missing end day
- January 1st for missing start month
- December 31st for missing end month

7.0 Demographics, Baseline Characteristics, Medical History, and Previous/Concomitant Medications

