Since subjects do not always adhere to the study visit schedule, the following rules will be applied to assign actual visits to protocol-specified visits including early termination visits. For each study visit mentioned in the protocol, a nominal or target day along with a window around the target day will be selected to represent the corresponding visit. Windows will be selected in a non-overlapping fashion so that a date collected on the CRF does not correspond to multiple visit windows. Moreover, windows will not discard

any post-baseline measurement recorded on the CRF. If a subject had two or more actual visits in one visit window, the visit closest to the target will be used as the study visit for that window. If two visits are equidistant from the target, then the later visit will be used for reporting. If more than one assessment is collected on the same day, then the average of those assessments will be used in analyses.

Table 1. Visit Windows for Analysis of Efficacy Variables, Laboratory Parameters and Vital Signs (Induction Study)

Scheduled Week	Nominal Day	Time Window (Rx Day A Range)
Week 0 ^a	1	≤ 1
Week 1	8	2 – 11
Week 2	15	12 – 22
Week 4	29	23 – 43
Week 8 ^a	57	44 – 71 ^b

Rx Day A = date of visit – date of first study drug injection in the Induction Study + 1

a. hs-CRP and fecal calprotectin collections are scheduled at Screening/Week 0 and Week 8 per protocol.

b. Minimum of Day 71 or the date of the first injection in the Maintenance Study, if applicable.

Table 2. Visit Windows for Analysis of Endoscopy Variables (Induction Study)

Scheduled Week	Nominal Day	Time Window (Rx Day A Range)
Week 0	1	≤ 1
Week 8	57	2 – 71 ^a

Rx Day A = date of visit – date of first study drug injection in the Induction Study + 1

a. Minimum of Day 71 or the date of the first injection in the Maintenance Study, if applicable.

Table 3. Visit Windows for Analysis of IBDQ, SF-36 and WPAI (Induction Study)

Scheduled Week	Nominal Day	Time Window (Rx Day A Range)
Week 0 ^a	1	≤ 1
Week 2	15	2 – 22
Week 4	29	23 – 43
Week 8 ^a	57	44 – 71 ^b

Rx Day A = date of visit – date of first study drug injection in the Induction Period + 1

- a. SF-36 and WPAI collections are scheduled at Week 0 and Week 8 per protocol.
- b. Minimum of Day 71 or the date of the first injection in the Maintenance Study, if applicable.

Definition of Missing Data Imputation

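### Maintenance visits are scheduled from the Week 0 dose but windowed from the first Maintenance injection, so a late enough start can leave an attended Week 52 Mayo assessment counted as missing

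*SAP*

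**What the plan says.** **Scheduling clock.** Maintenance SAP Section 4.2 states that "visit week designations will represent weeks since first adalimumab dose in the Induction Study". It allows plus or minus a "3 day window for all study visits", and asks sites to try to "bring subjects back to their original scheduled visit (calculated from Baseline").

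**Analysis clock.** Section 6.0 says that "Rx days are used to map actual study visits to the protocol specified study visits during Maintenance Study". Under each of Tables 1 to 6 it gives the formula "Rx Day = date of visit – date of first study drug injection in the Maintenance Study + 1". Table 1 puts Week 48 at Rx Days 261–295 (target 281) and Week 52 at 296–379 (target 309). When two visits share a window, the one nearer the target is used, and "If two visits are equidistant from the target, then the later visit will be used for reporting".

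**Related rules in Section 6.0 and Section 10.2.** Mayo data are assigned to a visit by the last diary day that entered the score. Diary days for bowel preparation, the endoscopy and the two days after it are dropped. A missing binary outcome is a failure, and a missing primary endpoint at Week 52 is no clinical remission. Endoscopy has its own Week 52 window, Rx Days 113–379 (Table 4).

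**How late Week 8 can be.** In the Induction SAP, the Week 8 window ends at Day 71, or earlier if Maintenance has begun: "Minimum of Day 71 or the date of the first injection in the Maintenance Study, if applicable".

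**The concern.** Table 1's target days match the visit schedule only for a subject whose first Maintenance injection falls on Day 57. If that dose is late and the subject then returns to the Baseline schedule, as Section 4.2 intends, every later visit has an Rx Day too small by the length of the delay. Some windows open only 6 days before target, so a correctly timed visit can land in the preceding one. At Week 52 the PGA and diary subscores would go to Week 48 while the endoscopy stayed at Week 52. The subject would have no Full Mayo score at Week 52 and would count as a non-remitter after attending the whole visit. This would touch the primary endpoint and ranked secondary endpoints 3, 4, 7, 9 and 10, all of which use Full Mayo remission at Week 52.

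**Working it through.** **1. Reproduce Table 1.** Target day = 7 × (week − 8) + 1; for Week 52, 7 × 44 + 1 = 309. Each upper bound is the midpoint of adjacent targets, rounded down; for Week 48, (281 + 309)/2 = 295. All 11 targets and all 10 internal bounds are reproduced.

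**2. Shift formula.** On the Week 0 schedule, week w falls on Day 7w + 1. With the first Maintenance dose on Day 57 + d and the visit e days early, Rx Day = (7w + 1 − e) − (57 + d) + 1 = target − d − e. For Mayo data subtract k as well. Diary days precede the visit, so k is at least 1.

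**3. Shift needed to leave a Table 1 window** (target − lower bound + 1):

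| Visits | Shift (days) |
|---|---|
| Weeks 12, 24, 37 | 7 |
| Weeks 10, 16, 52 | 14 |
| Weeks 29, 42 | 18 |
| Weeks 22, 35, 48 | 21 |

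**4. Inside the ±3 day windows.** By visit date the largest shift is 3 + 3 = 6, and nothing moves; Week 52 sits at 309 − 6 = 303. For Mayo data, 3 + 3 + 1 = 7 just reaches the limit for Weeks 12, 24 and 37.

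**5. Delay of 7 days, visits on schedule, by visit date.** Weeks 12, 24 and 37 fall on Rx Days 22, 106 and 197, in the windows for Weeks 10, 22 and 35. Each ties with the visit that belongs there, the later one is used, and Weeks 12, 24 and 37 are empty.

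**6. Week 52 by visit date.** At d = 13, Rx Day = 296, still Week 52. At d = 14 (Day 71), Day 365 gives 365 − 71 + 1 = 295, which is Week 48. The true Week 48 visit is at 281 − 14 = 267. Both are 14 days from 281, so the later is used and Week 52 is empty. With the visit 3 days early, d = 11 is enough: 309 − 11 − 3 = 295.

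**7. Week 52 Mayo data under the diary-date rule.** The documents do not give k. I assume k = 2 for a same-day endoscopy with one preparation day, and k = 5 for an endoscopy 3 days before the visit.

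| k | d needed, visit on time | d needed, visit 3 days early |
|---|---|---|
| 0 (visit date) | 14 | 11 |
| 1 | 13 | 10 |
| 2 | 12 | 9 |
| 5 | 9 | 6 |
| 8 | 6 | 3 |

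Only a diary gap of 8 days or more brings the loss inside the permitted visit windows, and then the gap contributes more than the clock.

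**8. Endpoints with their own tables.** Shift needed to lose Week 52: hs-CRP 309 − 275 + 1 = 35; calprotectin and IBDQ 309 − 258 + 1 = 52; endoscopy, EIM, SF-36 and WPAI 309 − 113 + 1 = 197. For hs-CRP, calprotectin and IBDQ, a delay of 7 to 13 days also leaves Weeks 12, 24 and 37 in place where collected.

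**9. Size.** Only would-be remitters can be lost. Section 4.3 assumes 30% and 48% remission. For each 1% of Week 8 responders whose Week 52 is lost (an assumed share), the rates fall by at most 0.30 and 0.48 points and the 18-point difference by 0.18, to 17.82. At an assumed 3%, the falls are 0.90 and 1.44 points and the difference is 17.46.

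**The case against.** - **The delay is extreme.** Visits have a ±3 day window, and Day 71 is the upper limit of a data-capture window, not permission to start Maintenance 14 days late. Week 10 itself is due on Day 71 (7 × 10 + 1). A subject never brought back to the Baseline schedule has larger Rx Days and is mapped correctly. This stands and keeps the problem rare at Week 52.
- **The SAP does not spell out how Full Mayo is assembled.** If it were treated as an endoscopy variable under Table 4, Week 52 would be safe. This partly stands. However, Table 1 is titled for efficacy variables, and the only placement rule for the Mayo score is the diary-date rule, so the loss is a natural programming result.
- **The first Maintenance dose is a legitimate anchor.** It measures time on re-randomised treatment, and the other clock has a mirror error: a Day 71 starter seen 14 days later, on Day 85, would fall in Week 12 (Days 79–99 from Week 0). This stands against re-anchoring every table.
- **Observed-case analysis is planned.** It does not help, because the subject is then left out at Week 52.

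A reader might infer that any late Week 8 costs the subject Week 52, that every efficacy endpoint is affected, or that one regimen is favoured. The documents support none of these. Week 52 needs a combined shift of 14 days, several endpoints have wider windows, and nothing suggests that the delay differs between arms re-randomised at Week 8.

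**Conclusion.** The two clocks are real and unreconciled, and the harm is limited. Weeks 12, 24 and 37 are exposed at a combined shift of 7 days, which for Mayo data is just reachable within the permitted visit windows; binary partial Mayo outcomes there become failures. Week 52 Mayo data are exposed at 14 days. With a diary gap of up to 2 days, that means a first Maintenance dose at least 9 days late, well outside the ±3 day window. Continuous Mayo endpoints become missing in the MMRM and are not scored as failures.

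This rests on Full Mayo being placed through Table 1, on subjects returning to the Baseline schedule, and on the assumed k. The documents do not show how many subjects start this late; the number is probably small. The expected result is a slight loss of remissions in both arms and a slightly smaller difference, with no bias towards either regimen. It is still worth correcting, because it affects the primary endpoint and is easily avoided.

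**What to change.** In Section 6.0 of the Maintenance SAP, let an attended scheduled visit keep its scheduled label. Say explicitly that at Week 52 the PGA, diary subscores and endoscopy stay together, and that the diary-date rule does not move them to another visit. Use Table 1's Rx Day windows for unscheduled and early-termination visits.

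Alternatively, count Table 1 from the Week 0 dose: Week 52 would have target Day 365 and window 352–435 (each bound + 56). This removes d, but e and k remain. Tables 2 to 6 need no change for Week 52.

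The cost is SAP wording and programming before database lock. A late starter's Week 52 value will reflect a little less than 44 weeks of maintenance; from Day 71 to Day 365 is 294 days, or 42 weeks. The Section 4.2 schedule already implies this.
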